13.0 Trial Procedures

13.1 Recruitment

A total of 105 adult male and female patients will be enrolled in this trial. Research personnel will identify potential subjects upon admission to the emergency department.

13.2 Participant identification

The trauma research fellow will attend all trauma admissions to the accident and emergency resuscitation department in order to screen participants for potential enrolment according to the study inclusion and exclusion criteria.

The trauma research fellow is a clinician by training, but not a member of the clinical team attending to the participant. This is due to the critical condition of participants, meaning that it is unlikely that a treating clinician will concurrently be able to provide the necessary care for the patient whilst also undertaking the research screening and enrolment procedures.

However, once the trauma research fellow deems a participant to be eligible for enrolment, they will confirm eligibility with the clinician leading the care for the patient (i.e. the trauma team leader) prior to enrolling the participant into the study. Our study centre and research team has experience in conducting similar screening procedures successfully in previous studies.

13.3 Informed Consent Procedures

Informed consent must be obtained prior to the participant undergoing procedures that are specifically for the purposes of the trial and are out-side standard routine care at the participating site (including the collection of identifiable participant data unless the trial has prior approval from the Confidentiality Advisory Group (CAG) and the Research Ethics Committee (REC)).

13.3.1 Responsibility for obtaining consent

The Principal Investigator (PI) retains overall responsibility for the informed consent of participants at their site and must ensure that any person delegated responsibility to participate in the informed consent process is duly authorised, trained and competent to participate according to the ethically approved protocol, principles of Good Clinical Practice (GCP) and Declaration of Helsinki. If delegation of consent occurs then details should be provided in the Site Delegation Log.

The trauma research fellow, who is a clinician by training, will be responsible for obtaining consent.

13.3.2 Consent Considerations

The right of a participant to refuse participation without giving reasons will be respected.

The participant must remain free to withdraw at any time from the trial without giving reasons and without prejudicing his/her further treatment and must be provided with a contact point where he/she may obtain further information about the trial. Where a participant is required to re-consent, for example if during the trial new Research Safety Information becomes available, or following an

amendment that affects the patient, or new information needs to be provided to a participant, it is the responsibility of the PI to ensure this is done in a timely manner.

13.3.3 Population

The study population will consist of adult male and female trauma patients with suspected active or ongoing haemorrhage.

13.3.4 Vulnerable participant's considerations

The PI takes responsibility for ensuring that all vulnerable subjects are protected and participate voluntarily in an environment free from coercion or undue influence.

13.3.5 Written/ reading / translation considerations

Participants who cannot read or write, require translators, or have cognitive impairment will be supported during the informed consent process. This includes allowing a witness to sign on a participant's behalf (in the case of problems with reading or writing) or allowing someone to date the form on behalf of the participant. In the case of participants who require verbal information to be provided in a different language, this will be done via telephone translation services or a hospital or personal interpreter.

13.3.6 Participants lacking capacity

Most, but potentially not all, subjects will be incapacitated at the time of eligibility (critical injury, mechanical ventilation, sedation), such that the Mental Capacity Act (England; 2005) and Declaration of Helsinki (World Medical Association; 2013) provide guidance. Patients will be enrolled within four hours of their injury and within two hours of admission to the accident and emergency department. This is a particularly stressful time for relatives and families, an important consideration when the intervention under investigation is time sensitive. This study requires the IMP to be given rapidly, thereby necessitating that eligible patients are consented very soon after hospital admission. As injury is an unexpected event, it is uncommon for relatives to be present at the time of hospital admission.

As stipulated by GCP the subject and/or their Personal LR (e.g. next of kin) should be given ample time to consider giving their consent for the study. It is felt that 24 hours is sufficient time for the patient and/or Personal LR to consider participation and give informed consent. However, the need for urgent treatment in this trial means implementation of the research cannot be delayed and it would be inappropriate to delay treatment until fully informed consent can be obtained from the patient or other nominated representative. Patients incapable of giving consent in emergency situations are an established exception to the general rule of informed consent in clinical trials.

As the timeframe required for subject or Personal LR consent is not compatible with the time sensitivity of this trial, several approaches to obtaining informed consent will be used. All are consistent with the Mental Capacity Act (England; 2005) and Declaration of Helsinki (2013).

Consent for initial enrolment in the trial will be sought from a Professional LR in the form of independent clinicians (trauma lead for the subject), who are familiar with the consenting process and present at every trauma call.

If Personal LRs are present, bearing in mind the clinical situation and their level of distress, they will be provided with brief information about the trial either verbally or in writing. Specifically, the investigator will explain to the relatives that the patient will receive the usual emergency treatments for traumatic haemorrhage but that in addition to these, the patient has been enrolled in a research study that aims to improve the outcome of patients with this condition.

It will be explained the study is being done to see whether using a drug called Artesunate will improve patients' outcome by protecting against organ failure. The relative will be informed that the patient will be given a single dose of Artesunate or placebo. The investigator will explain that whilst we hope that Artesunate will improve outcome after trauma haemorrhage, at present we cannot be sure about this. If the relative or representative objects their wishes will be respected. If no relatives are present, two doctors (one independent of the trial) will consider the patient's eligibility criteria and any known views of the patient about trial participation. Together they will decide whether or not to enrol the patient into the trial.

We do not propose to include a telephone contact with relatives/personal consultees in order to minimise stress and anxiety at a difficult time.

If and when patients regain physical and mental capacity to give consent, information will be provided to them and written informed consent will be sought for continuation in the trial. If a patient or representative declines to give consent for continuation at this stage, his/her wishes will be respected. For any patient included that did not regain full capacity, consent will be sought from a relative or other appropriate representative for continuation of the trial.

There is potential for a small group of research subjects to exist for whom a Personal LR is not available and who are subsequently unable to give consent due to death or permanent disability. In such cases Professional LR permission still stands in this situation and these subjects can remain within the trial.

In cases where the subject dies before the investigator has discussed the trial with the patient or the Personal LR, the patient can remain in the trial under the Professional LR consent from the Trauma Team Leader. We will not attempt future telephone contact with relatives/Personal LR in order to minimise stress and anxiety associated with the unexpected and traumatic death of their relative / next of kin. In cases where the investigator has made initial contact with the Personal LR prior to the subject's death but written agreement has not yet been obtained, then we will make a maximum of three further attempts (by any combination of telephone, e-mail or letter) to contact the Personal LR and obtain consent. If after these further attempts the Personal LR has not been contacted, then the subject shall remain in the trial based on the Professional LR consent.

In summary, we believe these approaches are justified under the conditions of the Mental Capacity Act (England; 2005) for the following reasons:

- 1. The urgent/emergency nature of the intervention.
- 2. The fact the IMP administered is already widely used in humans.
- The proposed recruiting centre has used this consenting procedure for previous randomised controlled trials in trauma (MP4OX Ph2b EudraCT: 2010-023129-39; Cryostat Ph2a ISRCTN55509212) and the ongoing ACIT-2 observational study (REC ref: 07Q0603/29) that has successfully recruited more than 1300 patients to date.

Prior to any study related activities and subsequently for continuation when the subject is capable or from a relative or representative, a copy of the Informed Consent Form approved by the Research Ethics Committee will be signed and dated. The original signed forms will be retained by the site in the study file, together with any subsequent approved amended versions. Copies of the original will be given to the subject or Personal LR for retention in their own records, and placed in the medical care records.

13.3.7 Minors

N/A

13.3.8 Consenting process

The trauma research fellow will be responsible for the consenting process, which will be conducted in the manner outlined in section 13.3.6. An assessment of capacity of the participant will be made according to the following criteria:

- Ability to understand the purpose and nature of the research.
- Ability to understand what the research involves, its benefits (or lack of benefits), risks and burdens.
- Ability to understand the alternatives to taking part.
- Ability to retain the information long enough to make an effective decision.
- Ability to make a free choice.
- Ability to make this particular decision at the time it needs to be made (though their capacity may fluctuate, and they may be capable of making some decisions but not others depending on their complexity)
- Where participants are capable of consenting for themselves but are particularly susceptible to coercion, it is important to explain how their interests will be protected.

The trauma research fellow will subsequently have a discussion with the participant (if and when they regain capacity) or his/her Personal LR (in the case of participants without capacity) about the nature and objectives of the trial, and the possible risks associated with their participation. They will also be provided with written information about the trial.

As stipulated by GCP, the participant should be given ample time to consider giving their consent for the study. 24 hours is the minimum period of time for an individual to consider their participation within the study. If for any reason, less than 24 hours is to be given, it will be documented why this is the case along with justification for this decision. The date that the Patient Information Sheet (PIS) is given to the participant or their Personal LR must be documented within the patient's notes to ensure that sufficient time is given.

13.3.9 Additional consent provisions for collection and use of participant data and biological specimens in ancillary studies

Blood samples will be drawn from participants at 6 time points for PK/PD analysis (See Section 13.8.3). Each draw will consist of a maximum draw of 10 mls. Any excess blood from this draw that is not required for PK/PD analysis will be processed and stored for future ethically approved research, provided the participant gives consent.

Specifically, SST[®] 5 mL vacutainer tubes (BD biosciences, UK) will be used to collect serum at each time point, which will be stored for later biomarker analysis and co-incubation with healthy donor peripheral blood mononuclear cells. This would allow exploration of mechanistic pathways behind

treatment with Artesunate and the influence that it has on circulating immunologically active mediators.

PAXgene[®] 2.5 mL vacutainer tubes (PreAnalytiX, Germany) will also be collected at 4 and 12 hour time points. Data generated from a rat haemorrhage model treated with Artesunate demonstrated increases in survival pathways (*Annals of Surgery, under review*). Genomic patient data generated will allow reverse translational research to further explore this phenomenon with our validated animal model. All samples will be labelled and stored in catalogued cryoboxes at -80°C immediately following processing.

Participants will be given the option to consent for these samples to be used for future research related to the conditions under investigation, including genetic research (but not research related to hereditary diseases). Samples and data will be de-identified prior to being shared with collaborators involved in this future research.

The decision to opt out of ancillary research will not affect a participant's ability to remain in the trial. Withdrawal from ancillary research will result in disposal of any obtained samples in accordance with Barts Health NHS Trust policy, and a note of their withdrawal will be made on the consent log.

13.4 Screening Procedures

Patients will be assessed for eligibility to enter the trial according to the defined inclusion/exclusion criteria upon arrival at the hospital. This will include a pregnancy test for all females of childbearing age. If patients are assessed to be eligible, consent for entry into the study will be sought. Data will be collected on all patients who are screened for eligibility on the study screening-log by the Trauma Research Fellows.

A screening log will be completed, which will record all patients considered for eligibility to the trial. The log will include date and time of screening, and the participant age, gender, and reasons for non-enrolment. The screening log will include patients approached but in whom consent was not obtained for the trial (with reasons). The screening log data will be reviewed at regular intervals.

The trauma research fellow and research assistant are responsible for completing the screening log after an eligible patient is identified and considered for participation in the trial

13.5 Patient Allocation

13.5.1 Randomisation Method

A simple randomisation method will be used as detailed below:

- First stage: subjects will be randomised to Low dose active or placebo on a 2:1 ratio.
- Second stage: subjects will be randomised to High dose active or placebo on a 2:1 ratio.

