11.6 Trial Design

This is a single-centre, randomized, placebo-controlled, parallel group study with a sequential groupdosing regimen (adaptive design). Its aim is to evaluate the safety and efficacy of Artesunate treatment compared to placebo, in addition to standard treatment, in severely injured trauma patients with traumatic hemorrhage. All subjects will be managed in accordance with local guidelines for traumatic hemorrhage.

Subjects will be assessed for eligibility upon arrival to the hospital. Due to the urgent/emergency nature of the intervention subjects will be recruited within 4 hours of their injury and within 2 hours of admission to the accident and emergency department. Eligible patients therefore need to be consented very soon after admission. As most, but potentially not all, subjects will be incapacitated at time of eligibility, consent can be obtained from relatives or if no relatives are present two

doctors (one independent of the trial) will decide on consent. If and when the subject regains physical and mental capacity they will be provided written information on the trial and will be given the opportunity to ask questions, informed consent will be sought for continuation in the trial. For any subject included but did not regain full capacity, consent will be sought from a relative or other appropriate representative for continuation in the trial.

Subjects will be randomized to one of three groups:

- Placebo arm (n = 35)
- Low Dose intervention arm: active drug 2.4mg/kg (n=35)
- High Dose intervention arm: active drug 4.8mg/kg (n=35)

The trial will be divided into two stages. The first stage will enroll patients into the Placebo (n=17) and Low Dose intervention arms (n=35), following which an interim analysis will be performed. The analysis will be limited to an analysis of safety data between the two groups. Provided there are no issues regarding safety or toxicity, the study will continue with the second phase enrolling patients into the high dose intervention arm (n=35) or placebo (n=18).

Each subject will be dosed and then remain in the study for 28 days or until they are discharged. There will be a 90-day follow-up though this will be conducted using data obtained via the NHS spine services (Health and Social Care Information Centre).

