19.9 Interim analysis and criteria for the premature termination of the trial

An interim analysis will be performed after recruitment of the first 52 patients. The analysis will be limited to an analysis of safety data between the two groups. Provided there are no issues regarding safety or toxicity, the study will be continued with an increased dose in the intervention arm.

At the interim analysis, a qualitative assessment of all recorded AEs and SAEs will be undertaken by the DMC to determine if the trial should be discontinued on account of safety concerns. AEs will be coded by system organ class (SOC) and preferred term (PT), using MedDRA. An overview of all AEs, SAEs, relationship to IMP, intensity and AEs leading to withdrawals or death will be presented by treatment group. AEs will be summarised using descriptive statistics. Treatment emergent AEs will be analysed separately.

The number and percentage of subjects with abnormal vital signs and/or laboratory values will be presented by treatment group. The data may also be presented as shift tables (normal, abnormal and not clinically significant, abnormal and clinically significant) with screening values as a reference.

The trial will be terminated following the interim analysis based on the safety data. The criteria for termination (e.g. total SAEs per group) shall be defined by the DMC. Outside the planned interim analysis the study will be terminated only on the grounds of new safety concerns or unforeseen recruitment issues.

The sponsor retains the right to stop the study, should the need arise.

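### Simple 2:1 randomisation within each stage cannot be relied on to give the fixed arm sizes (35/17, then 35/18) that the protocol states; a restricted list would

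*Protocol*

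**What the plan says.** Protocol section 13.5.1 gives the method and the ratio and nothing more: "A simple randomisation method will be used as detailed below". The detail is "First stage: subjects will be randomised to Low dose active or placebo on a 2:1 ratio" and "Second stage: subjects will be randomised to High dose active or placebo on a 2:1 ratio". Neither 13.5.1 nor 13.5.2 mentions blocks, a list with fixed totals, or minimisation. Section 13.5.2 adds only that an independent statistical consultant generates the codes and that allocations are opened from sealed envelopes.

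Section 11.6 states exact counts. For stage 1: "The first stage will enroll patients into the Placebo (n=17) and Low Dose intervention arms (n=35), following which an interim analysis will be performed". Stage 2 is described as "enrolling patients into the high dose intervention arm (n=35) or placebo (n=18", again as fixed numbers.

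Section 19.1 bases its power on those totals: 80% for 70 artesunate v 35 placebo, and 78% for each dose with 35 per arm, both for a 2-point difference in 48-hour SOFA with SD 3.43 and α = 0.05.

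Section 19.9 triggers the interim by a total: "An interim analysis will be performed after recruitment of the first 52 patients". It is a safety review only, described as "a qualitative assessment of all recorded AEs and SAEs will be undertaken by the DMC".

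**The concern.** Simple randomisation, in its usual meaning, allocates each patient independently. The ratio then holds on average and the arm counts are left to chance. The protocol therefore names a method that does not secure the numbers it states elsewhere.

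Placebo is the smaller group in each stage and the comparator for both doses, so a shortfall there matters most. Two things are exposed. One is the precision of the final comparisons. The other is the number of placebo patients behind the by-group safety tables, on which the decision to go on to the second stage rests.

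The two descriptions of the interim also part company. Section 11.6 places it after 17 placebo and 35 low-dose patients, section 19.9 after 52 patients. Under simple randomisation these are the same moment only if the split happens to be exact.

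**Working it through.** **Inputs.** Stage totals 52 (35+17) and 53 (35+18) from section 11.6; placebo probability 1/3 from the 2:1 ratio in 13.5.1; difference 2, SD 3.43 and α = 0.05 from 19.1. The per-dose tests are stated as one-sided. The pooled test has no stated sidedness; two-sided is assumed because it reproduces the stated figure.

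**1. The protocol's own power.** The standard error of the difference is 3.43 × √(1/n₁ + 1/n₂), and power comes from the noncentral t distribution with noncentrality 2/SE.
- 70 v 35: SE = 0.710, noncentrality 2.82, two-sided power 79.7% (stated 80%).
- 35 v 35: SE = 0.820, noncentrality 2.44, one-sided power 77.9% (stated 78%).

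Both reproduce.

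**2. Arm sizes under simple 2:1 randomisation.** The number on placebo is Binomial(n, 1/3).

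| | n | Mean | SD | 95% range | Chance of planned count |
|---|---|---|---|---|---|
| Stage 1 | 52 | 17.3 | 3.4 | 11 to 24 | 11.7% (17) |
| Stage 2 | 53 | 17.7 | 3.4 | 11 to 25 | 11.5% (18) |
| Overall | 105 | 35.0 | 4.8 | 26 to 45 | 8.2% (35) |

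The stage 1 chance is C(52,17) × (1/3)¹⁷ × (2/3)³⁵ = 0.1167. Both planned splits together: 0.1167 × 0.1145 = 0.0134, about 1.3%.

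**3. Placebo patients at the stage 1 review.** For Binomial(52, 1/3), P(11 or fewer) = 3.9% and P(13 or fewer) = 12.9%.

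**4. Power over the possible splits.**
- Pooled, 79 v 26: SE = 0.776, power 72.4%. Pooled, 60 v 45: SE = 0.676, power 83.4%. Averaged over Binomial(105, 1/3): 79.1%, against 79.7% as planned.
- P(26 or fewer placebo overall) = 3.7%; P(30 or fewer) = 17.6%, at which pooled power is 76.2% or lower. About 91% of draws keep pooled power at 75% or more.
- Per dose against all placebo patients, one-sided: average 77.3%, 95% range 73.0% to 80.8%, against 77.9% as planned.

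**5. What a restricted list would give.** A permuted list with fixed totals (35+17, then 35+18) gives the planned counts with certainty. Ordinary 2:1 blocks do not divide 52 or 53: 17 blocks of 3 make 51, so each stage ends inside a block. Blocks of 3 give the exact split with probability 0.67 in each stage. Blocks of 6 give it with probability 0.53 in stage 1 and 0.67 in stage 2. In either case the miss is at most one patient.

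**The case against.** The strongest reply is that this costs little. Average power falls by about 0.6 points in each comparison, near misses of 17 and 18 are harmless, and section 19.1 itself says that a formal sample size calculation is not possible. All of that stands. The 1.3% figure shows that method and numbers do not match; it does not measure harm.

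Three stronger readings are tempting, and the documents do not support them.

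- A reader might infer that each dose is compared only with its own stage's placebo, so that power could fall to 52% (41 v 11, one-sided). Section 19.1 plans each dose against 35 placebo patients, that is, both stages together. The within-stage figure also has the wrong baseline: the planned 35 v 17 already gives only 62%. It is not a fall from the stated 78%.
- A reader might infer that the interim formally depends on 35/17. Section 19.9 triggers it at 52 patients, makes it qualitative, and leaves the termination criteria to the DMC. No test depends on the split. What remains is that the by-group tables may have a thin placebo column.
- A reader might say that simple randomisation can never give the stated sizes. Each stage has about a 12% chance of doing so.

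"Simple" may also be meant loosely. Pre-generated codes in sealed envelopes are compatible with a list of fixed totals. But 13.5.1 names the method itself, and as written it disagrees with 11.6. If a restricted list was intended, one sentence settles the matter.

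Finally, simple randomisation is the hardest to predict, and here the person who prepares and gives the treatment is unblinded. That is a fair argument for it, and it bears on which restriction to choose.

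**Conclusion.** The point holds as a mismatch between the stated method and the stated numbers, with a small average cost and a moderate tail risk. It is not an error in the power calculation, whose figures reproduce. In about 4% of trials the draw would leave 26 or fewer placebo patients overall, with pooled power at about 72% or less. In about 13% it would leave 13 or fewer placebo patients at the stage 1 safety review.

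This rests on reading simple in its technical sense, on stages closing at 52 and 53 patients, on a two-sided pooled test, and on the protocol's own difference and SD. The risk is cheap to remove, so the sponsor should correct it before the list is made.

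**What to change.** In section 13.5.1, replace the reference to a simple method with restricted randomisation at 2:1 within each stage, in one of two forms:

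- a permuted list with fixed totals per stage (35+17, then 35+18), which gives the sizes in 11.6 exactly but does not control balance over calendar time within the stage; or
- concealed permuted blocks of randomly varying size (for example 3, 6 and 9), which hold the sizes closely, not exactly, and also balance over calendar time.

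The independent statistician who generates the codes should alone hold the block sizes or list structure. If blocks are chosen, 11.6 should call its arm sizes approximate. Sections 11.6 and 19.9 should then describe the interim trigger in the same terms.

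Neither form by itself secures 35 patients per arm with a 48-hour score. Section 13.9 replaces non-completers without saying which arm the replacement joins, so the list section should say how replacements are allocated.

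The cost is a few sentences and one list from a supplier already engaged. The downside is slight predictability, because the administrator sees the allocations. Concealed varying blocks limit it, as does a single long permuted list.
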